**[name] [name]**

**[name] [name]**

**Department of General Surgery, Westmead Hospital, NSW 2145**

---

Overview / Synopsis:

Surgical site infection (SSI) is the most common cause for health care associated infections (HCAIs) in patients undergoing surgery and is one of the best available surrogate measures of quality in surgery. SSI contribute to increased morbidity, mortality, scarring, delayed return to activities, impaired quality of life, increased health care costs, challenges in media, affects key performance indicators (KPI) and augments litigation.

Abdominal surgery, especially colorectal procedures are known to have higher risk of developing SSI compared with other operations, and therefore preventive measures are desirable. Incidence of incisional SSI in colorectal surgery is estimated to be between 5 – 45%. Laparoscopic surgery has been shown to significantly reduce wound infections in colorectal surgery but may not be applicable to all patients.

Over the last decade, there has been emerging evidence in success of topical negative pressure (TNP) dressings in prevention of SSIs. **However, there has been no randomised study to date to address its effectiveness in reducing SSI in abdominal surgery.**

The primary objective of this study is to assess the effectiveness of incisional TNP in reducing SSI following abdominal surgery. We also aim to ascertain rate of SSI in obese patients (BMI>30) and assess the effect of TNP in this subgroup, overall cost effectiveness of the intervention and effect of TNP on length of hospital stay. (TNP used in study will be **Prevena™ Peel & Place™ Therapy**, KCI Inc., USA)

**We propose to set the study up as a prospective randomised control trial.**

## Background (incl reference to relevant literature) / rationale:

Surgical site infection (SSI) is the most common cause for health care associated infections (HCAIs) in patients undergoing surgery. It is now considered by policy makers to be one of the best available surrogate measures of quality in surgery.

Abdominal surgery especially colorectal procedures are known to have higher risk of developing SSI compared with other operations, and therefore preventive measures are desirable. Incidence of incisional SSI in colorectal surgery is estimated to be between 5 – 30%, though some series have reported as high as 45% .

Laparoscopic surgery has been shown to significantly reduce wound infections in colorectal surgery but this approach is not applicable to all patients.

Consequences of SSI ,

- ✓ Patient – increased morbidity, poor scarring, delayed return to work / normal activities, impaired quality of life, increases risk of sepsis & mortality
- ✓ Hospital – prolonged hospital stay, increased health care costs, challenges in media
- ✓ Surgeon – affects key performance indicators (KPI), litigation

Obesity has been now recognised as a global health problem and its epidemic in increasingly taxing the health care systems worldwide. A recent article in JAMA Surgery identified obesity (body mass index, BMI  $\geq$  30) as an independent risk factor for SSI and reported an overwhelming 60% increase in wound infections after colectomy in this sub-group .

Negative-pressure wound therapy (NPWT) was introduced in 1994-95 by Kinetics Concepts Inc, KCI, USA as a form of therapeutic technique using a vacuum dressing to promote healing in acute or chronic wounds and enhance healing of first and second degree burns. It involves use of a vacuum device set at sub-atmospheric pressure over a specialised sealed polyurethane foam dressing . Vacuum assisted therapy VAC® therapy works by increasing tissue perfusion, reduces oedema and exudation, and promotes granulation tissue formation by facilitating cell migration and proliferation, thereby facilitating faster wound healing .

Over the last decade, there has been emerging evidence in success of topical negative pressure (TNP) dressings in prevention of SSIs . Retrospective comparative studies have demonstrated the superiority of incisional TNP over standard dressings in reducing incidence of SSI, seroma & hernia rates and wound dehiscence in high risk abdominal and reconstructive surgery . The NPWT theory is further supported by a recent multicenter prospective randomized clinical trial studying its use in high-risk wounds after severe skeletal trauma .

TNP used in study will be **Prevena™ Peel & Place™ Therapy**, KCI Inc., Australia. The first prospective RCT studying *Prevena™ Incision Management System* was published in 2011 by Pachowsky et al. This prospective, randomised study demonstrated decreased development of postoperative seromas in the wound and improved wound healing in surgical incisions for total hip arthroplasty . Two other recent comparative studies have shown the effectiveness of ‘Prevena™’ in reducing SSI in groin and post-sternotomy and following vascular and cardiac surgery respectively .

**However, there has been no randomised study to date to address effectiveness of TNP or in specific ‘Prevena™’ in reducing incisional SSI in abdominal surgery.**

### Study aims / objectives:

Our study is aimed to observe the effect of incisional topical negative pressure (TNP) dressing on surgical site infection (SSI) in patients undergoing open abdominal surgery.

Secondary objectives are, to evaluate the effect on

- Length of stay
- Cost-effectiveness
- Cosmetic outcomes
- Incisional hernias

### Hypotheses to be tested:

#### **Null hypothesis**

Early intervention with topical negative pressure dressing(s) does not reduce incidence of incisional surgical site infections in patients undergoing open abdominal surgery.

### Population / setting (anticipated number / ages / where / by whom):

#### **Setting**

Patients admitted to the Department of Surgery in Westmead (Public), Blacktown (Public), Norwest Private and Westmead Private Hospitals. Surgeons from the above hospitals, including those participating in Acute Surgical Roster will be invited to participate in our study.

#### **Inclusion Criteria**

1. Patients (over age of 16 years) undergoing elective and emergency laparotomy
2. Type of wounds - clean contaminated, contaminated and dirty

[Note: Patients who have had previous laparotomy including those who may have mesh implants in the site of proposed surgical incision and those patients with pre-existing stoma will also be considered for our study]

#### **Exclusion Criteria**

1. Patients who have hypersensitive allergy to silver
2. Patients who lack capacity to give / sign their own consent
3. Pregnancy
4. Patients with pre-existing 'open abdomen / laparostomy'

**Anticipated number**

**178 patients**

## **Type of study**

Prospective, non-blinded, randomised controlled study (RCT)

## **Methodology**

Informed consent will be taken from eligible patients participating in our study. Data will be collected prospectively on a standardised proforma (see *appendix i*) and then entered into a MS Excel database. A computer assisted randomisation will be used to assign patients to either the control (standard dressing) or interventional arm (TNP dressing). This will be made available to the operating surgeon only upon completion of skin closure to avoid performance bias. Wound closure will be by sutures or skin staples as per surgeon's preference. Stoma nurse(s) attached to our department will be independent assessor of the wounds. Wounds will be assessed on post-operative day 5-7 and again in 1 month's time. We propose to use SPSS for statistical analysis. We also aim to perform an intention to treat analysis in event of violation of research protocol.

Type of standard dressing (control arm)                      Standard Hospital Dressings  
(Comfeel / Cutiplast / Post-op Visible)

Type of TNP dressing (interventional arm)                      **Prevena™ Peel & Place™ Therapy,**  
(KCI, Australia)

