## **Definition of SSI (as per CDC Criteria) **

An infection is defined by the CDC as being the presence of at least one of the following:

1. Purulent drainage, with or without laboratory confirmation, from within the wound
2. Organisms isolated from an aseptically obtained culture of fluid from the incision
3. At least one of the following signs or symptoms of infection: pain or tenderness, localized swelling, redness and superficial incision deliberately opened by the surgeon, unless incision is culture-negative
4. Diagnosis of superficial incisional SSI by the independent assessor

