#### Logistics:

Enrolled patients will be assigned unique study number for purpose of data protection and confidentiality. Randomisation will be securely kept in a sealed envelope tagged onto consent form and be made available to surgeon upon completion of wound closure. The same will be made available by the study doctor(s) in the event of accidental loss of the sealed envelope (using the unique number). Patients who satisfy the entry criteria and consent to the study will be randomised in blocks of 8 to either control or intervention arm.

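### No masking is provided for the nurses who judge SSI, and one SSI criterion is their diagnosis alone, so the primary comparison is open to detection bias

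*Protocol*

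**What the plan says.** The synopsis sets the aim: "The primary objective of this study is to assess the effectiveness of incisional TNP in reducing SSI following abdominal surgery". Under Type of study the design is "Prospective, non-blinded, randomised controlled study (RCT", with no exception for outcome assessment.

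Methodology names the outcome assessors: "Stoma nurse(s) attached to our department will be independent assessor of the wounds". It also sets the timing: "Wounds will be assessed on post-operative day 5-7 and again in" one month. Nothing says that the nurses are kept unaware of the allocation at either visit.

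The one concealment step concerns the surgeon: "This will be made available to the operating surgeon only upon completion of skin closure to avoid performance bias". Logistics adds the mechanism: "Randomisation will be securely kept in a sealed envelope tagged onto consent form". The protocol does not say where the opened slip goes afterwards.

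The Definition of SSI section sets the counting rule: "An infection is defined by the CDC as being the presence of at least one of the following". The fourth item is "Diagnosis of superficial incisional SSI by the independent assessor".

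**The concern.** Independence and masking are different safeguards. A nurse may have no part in the operation and still know which dressing the patient had. Here the assessors belong to the department running the trial, and the design is declared open without reserving outcome assessment.

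The SSI definition adds to the exposure. Criterion 4 needs no pus, culture or opened wound, so the assessor's view is enough for a case. Criteria 1 and 3 also involve bedside judgement; criterion 2, the culture, is the most objective.

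If judgement leans with knowledge of the arm, the two arms are measured differently. A lean towards TNP raises the false-positive rate and exaggerates the benefit. Power and sample size estimation anticipates a relative reduction of about 80%, and Study procedures says that the manufacturer funds the devices, so a favourable result will be examined on exactly this point. Who assesses the outcome, whether masked, and what counts as a case are design matters. A statistical analysis plan cannot restore masking once the wounds have been judged.

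**Working it through.** **Inputs from Power and sample size estimation:** control rate 0.15, TNP rate 0.03, two-sided 0.05, 80% power, 89 per arm.

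**The plan's own figure.** For a chi-square test without continuity correction, with mean rate 0.09:

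n = [1.960·√(2 × 0.09 × 0.91) + 0.842·√(0.15 × 0.85 + 0.03 × 0.97)]² / 0.12² = 88.1, rounded up to 89 per arm.

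The normal-approximation power at 89 is 80.4%, and the odds ratio is (0.03/0.97)/(0.15/0.85) = 0.175. The stated sample size reproduces. It takes SSI as measured equally well in both arms.

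**Bias model (all error rates are assumptions).** Let the true SSI rate p be the same in both arms. Let u be the share of uninfected control wounds called SSI, and m the share of TNP infections not counted. The observed rates are:

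- control = p + (1 − p)u
- TNP = p(1 − m)

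Example with p = 0.09, u = 0.05, m = 0: control = 0.09 + 0.91 × 0.05 = 0.1355 and TNP = 0.09. The apparent relative reduction is 1 − 0.09/0.1355 = 34%.

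The chance of p<0.05 is the exact binomial rejection probability of the uncorrected two-sided chi-square test at 89 per arm. Ranges are over p = 9%, 12% and 15%.

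| Controls over-called (u) | TNP infections missed (m) | Chance of p<0.05 with no true effect | Apparent relative reduction |
|---|---|---|---|
| 0 | 0 | about 5% | 0% |
| 3% | 0 | 7-9% | 15-23% |
| 5% | 0 | 11-16% | 22-34% |
| 10% | 0 | 30-43% | 36-50% |
| 3% | 20% | about 18% | 32-39% |
| 5% | 30% | about 37% | 45-54% |

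**Which route criterion 4 opens.** Because one criterion is enough, criterion 4 can only add cases. It cannot cancel pus, a positive culture or an opened wound. The rows with m = 0 are therefore the ones it opens directly. The last two rows also need infections to be missed in the TNP arm, mainly through judgement on criteria 1 and 3 or through fewer cultures.

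**In patients.** At p = 9%, u = 5% is 89 × 0.91 × 0.05 = 4.1 control wounds, and u = 10% is 8.1.

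**The case against.** **The text does not say that the nurses know the arm.** True. It is inferred from the non-blinded label and the absence of any masking step. The inference is fair, because masked assessment in an otherwise open trial is a feature that a protocol would state.

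**The list of criteria is presented as the CDC definition.** It is, and the point is not that criterion 4 is illegitimate. A recognised definition does not mask the person who applies it.

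**The direction and rates of error are assumed.** This stands. The documents give no misclassification rate and say nothing of the nurses' expectations. Over-calling equally in both arms would not favour TNP. The table shows sensitivity, not a forecast.

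Some stronger readings are tempting but not supported:

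- *Detection bias could account for the whole planned effect.* The scenarios above give apparent reductions of at most 54%, against 80% planned. Reaching 15% versus 3% with no true effect takes extreme error. With a true rate of 15%, 80% of TNP infections would have to be missed. With a true rate of 3%, (0.15 − 0.03)/0.97 = 12.4% of uninfected control wounds, about 11 patients, would have to be over-called.
- *A few opinion-only calls decide the result.* Over-calling 3-5% of controls alone gives 7-16%, not 18-37%.
- *The allocation is visible in the notes, or the device is on the wound when it is assessed.* The protocol does not say where the opened slip is filed or whether the nurse uses the consent form. It states no wear time for the TNP dressing. Earlier inspection or swabbing of control wounds is likewise undocumented.
- *No analysis can help.* Masking cannot be restored afterwards, but an analysis on criteria 1-3 removes the cases that rest on opinion alone.

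**Conclusion.** The point holds in a limited form. In a trial declared non-blinded, the protocol provides no masking for the assessors of the primary outcome and lets their diagnosis alone count as a case. Concealment until skin closure does not reach this.

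With no true effect, a true rate of 9-15% and 89 per arm, over-calling 3-10% of uninfected control wounds lifts the false-positive rate from about 5% to between 7% and 43%. Adding missed TNP infections gives about 18% to 37% in the two combinations examined. These figures depend on assumed error rates and on error that favours TNP. They show inflated false positives and an exaggerated benefit, not a demonstration that bias would yield the planned 80% reduction. The gap should be closed before wounds are assessed, because it cannot be closed afterwards.

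**What to change.** State in Methodology that:

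- the stoma nurse is not told the allocation;
- the nurse assesses the wound only after someone else has removed the dressing as already scheduled, and assesses masked in every case at the 1-month visit;
- the opened allocation slip is kept out of the papers the assessor uses;
- each SSI is recorded with the criterion or criteria met, and each assessment with whether the assessor had become unmasked (the data proforma is not shown and may already hold part of this);
- a sensitivity analysis counts SSI on criteria 1-3 only.

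Two measures should be avoided. Counting criterion 4 only when masking held would make the endpoint depend on unmasking. If dressing marks unmask more TNP wounds, TNP cases would be discarded selectively. Nor should wound cleaning before assessment be prescribed: that is bedside care, and it could remove the pus that criterion 1 relies on.

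The cost is small. Staff, visits and the 89 per arm are unchanged; the additions are an order of events at the bedside, a filing rule and a few recorded items. Two downsides remain: dressing marks may unmask some day 5-7 assessments, and the criteria 1-3 analysis will have fewer events and so less precision.

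### Intention to treat is worded as an additional analysis, conditional on protocol violation, and no primary analysis set is named, so patients could be left out after their allocation is known

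*Protocol*

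**What the plan says.** On the analysis set, the Methodology section has one sentence: "We also aim to perform an intention to treat analysis in event of violation of research protocol". It follows the statement that SPSS will be used. No section names the set that carries the primary comparison, and no per-protocol or as-treated set is mentioned.

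On entry, the Inclusion Criteria require "Patients (over age of 16 years) undergoing elective and emergency laparotomy" and "Type of wounds - clean contaminated, contaminated and dirty". Clean wounds are not listed.

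On allocation, the Logistics section says "Randomisation will be securely kept in a sealed envelope tagged onto consent form and be made available to surgeon upon completion of wound closure", and also "Patients who satisfy the entry criteria and consent to the study will be randomised in blocks of 8 to either control or intervention arm". Methodology gives the same timing of disclosure: "This will be made available to the operating surgeon only upon completion of skin closure to avoid performance bias".

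The design is given under Type of study as "Prospective, non-blinded, randomised controlled study (RCT)". The planned size is 178, which is 89 per arm.

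**The concern.** In a randomised superiority trial the main comparison should keep every randomised patient in the allocated arm. The protocol's sentence is weaker in three ways: the analysis comes in addition to something, it is an aim, and it is triggered by a violation. With no primary set named, an analyst could report a comparison without the violators as the main result, add intention to treat beside it, and remain within the plan.

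The route to bias lies after the envelope is opened. The people deciding what counts as a violation may know the arm. Either kind of dressing can come off, but only the TNP arm has a vacuum device that can fail or be stopped early. Violations are therefore likely to be unequal between arms, and may be related to the state of the wound. Leaving out TNP patients for such reasons could remove infected wounds from one arm only.

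A second, smaller gap concerns when a patient becomes a trial patient. The envelope is attached to the consent form, yet two entry criteria, laparotomy and wound class, may be settled only at operation. The protocol does not say whether someone who then proves ineligible has been randomised.

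**Working it through.** **1. The plan's own figure.** Inputs from Power and sample size estimation: control rate p1 = 0.15, TNP rate p2 = 0.03, two-sided alpha 0.05, power 80%, two-group chi-square test. The mean rate is 0.09.

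n per arm = [1.960 × √(2 × 0.09 × 0.91) + 0.8416 × √(0.15 × 0.85 + 0.03 × 0.97)]² / (0.15 − 0.03)²
= [1.960 × √0.1638 + 0.8416 × √0.1566]² / 0.0144
= 1.1263² / 0.0144 = 88.1, rounded up to 89.

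The stated 89 reproduces (power 80.4%), so the sample size is not in error. It matches the version without continuity correction, and the same test is used below.

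**2. Expected events.** 89 × 0.15 = 13.35 and 89 × 0.03 = 2.67, about 16 in all.

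**3. Effect of removing infected TNP patients.** For a table with a infected and b uninfected controls, and c infected and d uninfected TNP patients, the uncorrected statistic is X² = N(ad − bc)² / [(a+b)(c+d)(a+c)(b+d)].

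- 13/89 v 6/89: 178 × (13×83 − 76×6)² / (89×89×19×159) = 2.887
- 13/89 v 5/88: 177 × (13×83 − 76×5)² / (89×88×18×159) = 3.858

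| Control | TNP | How reached | p |
|---|---|---|---|
| 13/89 | 6/89 | chosen borderline case | 0.089 |
| 13/89 | 5/88 | one infected TNP patient removed | 0.0495 |
| 13/89 | 4/87 | two removed | 0.025 |
| 13/89 | 3/89 | about the planned split | 0.009 |
| 13/89 | 2/88 | one removed from the planned split | 0.003 |

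The first three rows cross 0.05 and the last two do not. The crossing also depends on the test: for 13/89 v 5/88, p is 0.086 with continuity correction and 0.079 to 0.080 by Fisher's exact test. If the TNP rate really is 3%, six or more infections among 89 has a binomial probability of about 5%.

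**4. Cost in numbers.** The total of 178 is 2 × 89, with no margin for exclusions. The documents give no exclusion rate. If 5%, 10%, 15% or 20% were dropped evenly from both arms (assumed), power at 15% v 3% would be 78.3%, 76.1%, 73.7% or 71.0%.

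**5. Order of events.** Logistics puts the entry criteria and consent before randomisation, but also attaches the envelope to the consent form and has it opened at wound closure. Whether laparotomy was done, and the wound class, should be known by then. A patient found ineligible at that point can be set aside with the envelope still sealed. If the seal holds, that decision cannot depend on arm.

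**The case against.** The strongest defence is that the sentence can be read more mildly. It follows the remark about SPSS, so its opening may only add a second statistical intention. Intention to treat differs from other sets only when there are violations, so the condition may simply mean that violators are analysed as randomised. No per-protocol set is named anywhere, and full definitions of analysis sets are often left to a statistical analysis plan, which is not at hand. This stands to the extent that a reader might infer that the protocol makes a per-protocol analysis primary, and the document does not say so. It does not remove the point: the protocol makes a statement on the matter, and that statement permits either reading.

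A reader might also infer that patients with clean wounds, or without a laparotomy, will be randomised and then excluded in a way that favours TNP. The documents do not support this. The timing of wound class is an inference, Logistics puts eligibility first, and the allocation stays sealed until skin closure. Skin left open is not an exclusion criterion either, since only a pre-existing open abdomen or laparostomy is excluded. If the skin is never closed, the trigger for opening the envelope does not occur, which is a procedural gap and not an arm-specific exclusion.

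The third objection is that the illustration uses a chosen borderline split, 13 v 6, where the planning rates imply about 13 v 3. That is correct. The illustration shows sensitivity near 0.05, not what is likely to happen.

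**Conclusion.** The point holds as a defect of wording with a real consequence. The plan neither schedules nor rules out exclusions made after allocation is known, and its only sentence on the subject leaves a primary result without those patients compliant. One arm-related exclusion can move p from 0.089 to 0.0495, but only for a borderline split and under the uncorrected test. At the planned split the conclusion is unchanged, so a general claim that one or two exclusions would reverse the result goes too far.

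The undefined moment of randomisation is secondary. On the assumption that envelopes stay sealed until closure, its effect is on numbers and on balance within the blocks of 8, not on bias between arms. How many patients it would affect cannot be known from the protocol.

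This should be fixed, but the documents do not support treating it as a flaw that invalidates the trial.

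**What to change.** Replace the Methodology sentence with: *The primary analysis is by intention to treat and includes every patient whose allocation was opened, in the allocated arm, whatever dressing was worn; per protocol is supportive.*

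In Logistics, define randomisation as the opening of the allocation after skin closure, once wound class and eligibility have been recorded. A patient found ineligible before that is logged as not randomised. Account for every unopened envelope, with the reason, and say how it is handled within its block.

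The existing sealed, individually numbered envelopes can stay. The cost is a change of wording, one extra record in theatre before opening, and a log of unopened envelopes. The target of 89 per arm should then count opened allocations. No change to the design or the sample size calculation follows from this point.
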